That dosage is significantly higher than recently described in a Danish uni-center quality study of 100 patients ([name] 2023). Among these patients, 85 received the standard postoperative pain management for cesarean section, which aligns with the pain treatment protocols employed in most hospitals across the country: A fixed dose of paracetamol and NSAID, supplemented with oral morphine; nerve blocks or intrathecal morphine are not given routinely. The median 24-hour oral morphine equivalent dose given to the patients by request to the nurses was 30 mg (IQR: 20-50). The relatively lower opioid dose may suggest an existing underestimation and suboptimal treatment of the patients' pain. At 6, 12, 18 and 24 hours after the cesarean section the reported average NRS (0-10) pain scores during movement were 7,

6, 6, and 5 respectively, corresponding to moderate or severe pain, and further supports the possibility of underestimation and undertreatment of post-cesarean pain.

In a Danish multicenter survey conducted in 2020 to 2021 (Lindelof 2022), 861 cesarean section patients were asked 24-48 hours after surgery how much they agreed on having “experienced severe pain after the cesarean section” In this assessment, 45% scored ≥ 8 (NRS 0-10).

Overall, there is strong indications that currently a substantial number of women in Denmark experience severe pain in the first days after their cesarean section. To address this, we have established an obstetric-anesthesiologic research cluster as part of the national perioperative research network, CEPRA (Nørskov et al. 2023) with an aim to optimize pain treatment for the approximately 12,700 Danish patients who undergo cesarean section every year.

Objective

This study aims to map postoperative pain in Danish patients undergoing elective cesarean section. Specifically postoperative pain levels, impact on physical function, side effects from pain medication, and treatment approaches in the postoperative period.

Furthermore, we aim to test the feasibility of repeated SMS-based questionnaires sent to the patients in the postoperative period. Based on response rates and frequency of outcomes, data from this observational study will also be used to inform a randomized controlled multicenter trial aiming to test better postoperative pain interventions for cesarean section patients.

Method

Study design

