Prospective Danish multicenter cohort study based on patient-reported outcomes (SMS-based questionnaires) and clinical data from electronic health records.

Inclusion criteria

Patients who undergo planned cesarean section under spinal anesthesia.

Patients who speak and read Danish and can provide informed consent to participate.

Patients who have a smartphone that can receive an SMS with a link to a questionnaire that can be accessed on an online website on the phone.

Exclusion criteria

Age < 18 years

Number of participants

Minimum 400 patients, included from minimum 9 centers representing all 5 regions in Denmark.

Outcomes

Outcomes have been selected to align with the outcomes in a subsequent randomized controlled multicenter trial, where we will investigate whether the addition of intrathecal morphine provides better postoperative pain control. Therefore, opioid side effects are given high priority in the outcome measures.

The following abbreviations are used in the section outcome measures:

Time intervals are specified as the time difference from the administration of the spinal anesthesia (t0), and outcomes are assessed either through patient questionnaires (P) or by reviewing medical records (J).

Outcome measures

Maternal outcomes

Primary outcomes

- Level of pain during the activity from lying to a seated position, after 24 hours. NRS 0-10 (P)
- Morphine associated adverse events within 24 hours after CS, assessed as a binary outcome including nausea, vomiting, dizziness, itching, or urine-retention (P). Vomiting and urine-retention, will be reported as yes/no. Nausea, dizziness and itching will be assessed as “none”, “little”, “moderate”, or “severe”, with patients reporting “moderate” or “severe” categorised as having a positive outcome.

Secondary outcomes

- Opioid consumption within the first 24 hours after caesarean section (oral morphine equivalents, mg) (J)
- Insufficient spinal anesthesia related adverse events during the caesarean section, as binary composite outcome of the proportion of patients in need of conversion to general anesthesia, intraoperative opioids, sevoflurane, or nitrous oxide for intraoperative pain, or repeated neuraxial procedure (spinal or epidural placement following failed spinal). (J)
- Level of pain during the activity from a lying to a seated position, after 6, 12, 18 hours. NRS 0-10 (P)
- The ability to mobilize independently at 24 hours after surgery. Yes/No (P)

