- Obstetric Quality of Recovery score using Obs-QoR-10 (Pervez Sultan et al. 2020; P Sultan et al. 2020)

How much have you been bothered by this problem in the past 24 hours?

1. Pain. 24 hours. None-worst imaginable 0-10. (P)
2. Nausea or vomiting. 24 hours. None-worst imaginable 0-10. (P)
3. Dizziness. 24 hours. None-worst imaginable 0-10. (P)
4. Shivering. 24 hours. None-worst imaginable 0-10. (P)
5. I have been comfortable. 24 hours. Not at all - all the time 0-10. (P)
6. I am able to mobilize independently. 24 hours. Not at all - all the time 0-10. (P)
7. I can hold my baby without assistance. 24 hours. Not at all - all the time 0-10. (P)
8. I can feed/nurse my baby without assistance. 24 hours. Not at all - all the time 0-10. (P)
9. I can look after my personal hygiene in the past 24 hours. 24 hours. Not at all - all the time 0-10. (P)
10. I feel in control in the past 24 hours. 24 hours. Not at all - all the time 0-10. (P)

- Global Health Score (Euroqol 2023) 24 hours. Worst-best imaginable health state 0-100 (for validation of Obs-QoR-10) (P)
- Response rates for questionnaires after 6,12,18,24,48 hours plus 7 and 30 days after the cesarean section.
- Response time for questionnaires after 6,12,18,24,48 hours plus 7 and 30 days after the cesarean section.

Neonatal outcomes

Primary outcome

- Need for neonatal admission within 24 hours (yes/no). (J)

Secondary outcomes

- Infants in need of respiratory support within 48 hours (continuous positive airway pressure treatment, positive pressure ventilation, HNF (nasal high flow), intubation or oxygen therapy). Yes/No and time (J)
- Proportion with established breastfeeding at 30 days following delivery, if intended. (P)

Exploratory outcomes

- Apgar score at 5 minutes. (J)
- Apgar score at 10 minutes. (J)
- Proportion of infants with Apgar <7 at 5 minutes. (J)
- Readmission within 24 hours after discharge. Yes/No.
- Readmission within 7 days after discharge. Yes/No.

Development and validation of questions:

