The Research Ethics Committee (VEK) and the regional research ethics committee for the Capital Region of Denmark (Region Hovedstaden) have been presented with the project description and protocol and have waived the need approval due to Danish legislation. Case number F-23004686. (See Appendix 1)

Informed consent

Verbal informed consent is obtained during the inclusion process with each patient. The patient must consent to receive questionnaires on the mobile phone and to the data manager accessing the medical records related to the cesarean section for the patient and the baby. The patient is informed that participation is voluntary and that their data will be securely stored. Written description of the consent is electronically sent to the patient, including a description of how to withdraw consent. This is approved by the data protection authority for the Capital Region of Denmark (Region Hovedstaden) with case number P-2023-90

Data Processing and statistics

All data will be handled in the secure REDCap database. Descriptive statistics will be used to analyze data. Continuous data will be summarized as median (interquartile range) or mean if the data is normally distributed. We plan to do a subgroup analysis on the groups where intrathecal morphine or TQL block has been administered. And categorical data as frequency (percentage). We will try to minimize missing data as much as possible, by sending questionnaires directly to the participants mobile phones. Number of missing data will be accounted for when describing data. Sample size is determined by convenience. The study is designed to be as large as possible, as all hospitals in Denmark, handling elective cesarean sections, will be invited to participate. Larger sites (>300 elective CS per year) commits to include 50 patients, medium scale sites (200-300 elective CS per year) commit to include 40 patients, and smaller sites (<200 elective CS per year) commits to include 30 patients.

Collaboration Agreement

A collaboration agreement has been established between project leaders and site coordinators, outlining mutual obligations and rules for data usage.

Inclusion Period

01.09.2023-31.12.2024, 1-6 months depending on the rate of inclusion at different sites.

Participating Departments

Maternity units from all 5 Danish regions. The following hospitals have agreed to participate:

Capital Region of Denmark (Region Hovedstaden): Hilleroed, Herlev, Hvidovre, Rigshospitalet

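### A count of missing replies and a response rate cannot show whether women who do not answer at 24 hours differ from those who do, for the two patient-reported maternal primary outcomes

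*Protocol*

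**What the plan says.** In the protocol, Data Processing and statistics, the analysis is set out in one line: "Descriptive statistics will be used to analyze data". Continuous data get a median with interquartile range, or a mean if normally distributed; categorical data get a frequency and percentage. On missing data, the section relies on sending questionnaires straight to the woman's phone to limit losses, and then states: "Number of missing data will be accounted for when describing data". The one further analysis named is a subgroup analysis by intrathecal morphine or TQL block, which does not involve reply status.

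Under Primary outcomes, both maternal primary outcomes (24-hour pain on moving from lying to sitting, and the adverse-event composite within 24 hours) are marked as patient-reported. The neonatal primary outcome comes from the record and is not affected.

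Non-response itself is measured. The Exploratory outcomes include "Response rates for questionnaires after 6,12,18,24,48 hours plus 7 and 30 days after the cesarean section" and response time at the same seven points. The Objective section adds that "we aim to test the feasibility of repeated SMS-based questionnaires sent to the patients in the postoperative period".

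**The concern.** The Objective section says: "This study aims to map postoperative pain in Danish patients undergoing elective cesarean section". The descriptive figure is therefore the result itself, and any difference between women who reply and women who do not falls directly on it. A woman who is in pain, nauseated or drowsy a day after surgery may be less likely to answer, or more likely. The planned outputs say how many answered and how fast. They do not say whether the 24-hour figures hold for those who did not answer.

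The frequency of outcomes also has a second use: "Based on response rates and frequency of outcomes, data from this observational study will also be used to inform a randomized controlled multicenter trial". A distorted adverse-event proportion would carry over into that planning.

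Data that bear on the question are already being collected. The same movement-pain item is asked at 6, 12 and 18 hours, as are nausea, dizziness and itching. Whether or not a woman replies, the record gives spinal morphine (Anesthesia information) and 24-hour opioid dose, nerve block or epidural, and itch treatment (Pain management). Consent covers the record review. The protocol does not put any of these to use in checking the two primary outcomes.

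**Working it through.** **Figures in the plan.** There is none to reproduce. The minimum of 400 is a convenience sample, and no response rate or precision is stated. That the summaries describe only women who reply is an inference, since no denominator is named. Everything below is illustrative.

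**Simple identity.** Bias of the respondent value = share not replying × (responder value − non-responder value).
- 20% not replying, difference of 2 NRS points: 0.20 × 2 = 0.4 NRS points.
- 20% not replying, difference of 20 percentage points: 0.20 × 20 = 4 points. The 95% half-width of a proportion near 50% with 320 replies is 1.96 × √(0.25/320) = 5.5 points.
- 5% not replying: 0.05 × 2 = 0.1 NRS points, and 0.05 × 20 = 1 percentage point.

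**Movement pain, mean.** From the protocol: N = 400 and the pilot movement means 7, 6, 6 and 5 at 6, 12, 18 and 24 hours (Background). Assumed: SD 2.3, correlation 0.5-0.7 between time points, scores rounded to 0-10, and odds of non-reply multiplied by 1.1 to 1.65 per NRS point, in either direction. Non-reply at 24 hours depends either on the 18-hour score or on the unseen 24-hour score. Bias is the simulated respondent mean minus the full-cohort mean, in absolute value. SE = 2.3/√(number replying).

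| Response | SE | Follows 18-hour score | Follows 24-hour score |
|---|---|---|---|
| 95% | 2.3/√380 = 0.118 | 0.01-0.08 (0.1-0.7 SE) | 0.02-0.12 (0.2-1.0 SE) |
| 80% | 2.3/√320 = 0.129 | 0.05-0.29 (0.4-2.3 SE) | 0.10-0.43 (0.8-3.3 SE) |
| 70% | 2.3/√280 = 0.137 | 0.07-0.43 (0.5-3.1 SE) | 0.14-0.64 (1.0-4.7 SE) |

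With non-reply completely at random, the simulated bias was 0.003 or less.

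**Movement pain, median.** In the same model, the respondent median equalled the full-cohort median in at least 99% of cohorts at 95% response and in about 69-99% at 80%. At 70% with the steepest dependence on 24-hour pain, it moved in about 78%. The quartiles moved by a point more often. Both results partly reflect the set-up. A true mean on a whole number steadies the median. The true quartiles, 5 ± 0.674 × 2.3 = 3.45 and 6.55, lie next to rounding boundaries.

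**Adverse events.** Assumed: true rate p = 0.40, and odds of non-reply 1.5 to 3 times higher, or lower, with an event. Observed rate = p(1 − P(miss | event))/(1 − m), where m is the share missing. Worked case, m = 0.20 and odds ratio 2: P(miss | event) = 0.268 and P(miss | no event) = 0.155. Check: 0.4 × 0.268 + 0.6 × 0.155 = 0.20. Observed = 0.4 × 0.732/0.8 = 0.366, a bias of 3.4 points; SE = √(0.4 × 0.6/320) = 2.7 points. Over the whole range the bias is 0.5-1.3 points at 95% response, 1.9-5.4 at 80% and 2.9-8.0 at 70%. Best/worst-case bounds around an observed 40%, from (1 − m)p to (1 − m)p + m, are 38-43%, 32-52% and 28-58%.

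**What the remedies can do.**
- Adjusting for the 6, 12 and 18-hour replies leaves at most about 0.01 NRS of bias in the mean if non-reply follows the 18-hour score. If it follows the 24-hour score, 0.04-0.29 remains at 80% response and 0.06-0.43 at 70%.
- If half the non-responders also lack earlier replies (odds ×1.35-1.65), 0.07-0.22 and 0.20-0.53 remain. These ranges run across the two response levels, for dependence on the 18-hour and the 24-hour score respectively.
- In a responder/non-responder table at 80% response, with non-reply following 24-hour pain, the gap on the 18-hour score is 0.7-1.5 NRS points at odds ×1.35-1.65. Its 95% interval excludes zero in 70-100% of cohorts (47-98% if half lack earlier replies). The figure falls to 41-70% at ×1.2 and 14-24% at ×1.1, and is about 5-6% with no dependence.

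**The case against.** The strongest reply is that this asks for an addition. Responder tables, imputation and bounds often sit in an analysis plan, which is not shown here. The sentence on missing data is true, is not exclusive and does not assume that replies are missing at random. The study makes non-response visible by design, tests no hypothesis and is open about its convenience sample.

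Much of this stands. An unseen plan could contain the check, and the protocol contains no contradiction here. A reader might infer that the protocol ignores missing data; it does not. What remains is that the protocol states an approach, a count alongside descriptive summaries, and that approach cannot answer the question the study's own aim raises.

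It is also fair that every missingness input is assumed, and that the pain figures concern the mean while the protocol names the median first. The adverse-event proportion has no such protection.

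A reader might infer that the results will understate pain. The protocol gives neither a response rate nor a direction, so that is not supported. A reader might also infer harm to the later trial's sample size for pain. In the same simulations the respondent SD falls by at most about 4% (non-reply following 18-hour pain) or 8% (following 24-hour pain), so no such claim is made. Nor would the proposed table reveal unseen 24-hour scores: it shows differences on observed features only, and women who never reply contribute record data alone.

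**Conclusion.** The point holds as a limitation of the stated approach, at the level of an inexpensive improvement. The planned outputs quantify non-response but do not show whether it is selective. Whether the two estimates are in fact biased, and which way, cannot be known from the protocol.

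With about 95% response the matter is negligible. With 70-80% response and moderate to strong dependence of reply on pain or symptoms, the bias in the mean or in the adverse-event proportion could exceed one standard error; with weak dependence it mostly would not. The median is less sensitive than the mean, the quartiles or the proportion. This rests on the assumed SD, correlations, response levels, odds of non-reply and event rate; only the sample size and pilot means come from the protocol. Confidence is moderate, chiefly because a separate analysis plan may already cover the point.

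**What to change.** Keep the observed summary, the number missing and the response rate as the main result. Add to Data Processing and statistics:

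- (a) A table of 24-hour responders against non-responders on site, intrathecal morphine, 24-hour opioid dose, nerve block or epidural, itch treatment, and their available 6, 12 and 18-hour replies. State that it shows differences on observed features only.
- (b) One sensitivity estimate of 24-hour movement NRS, in the same summary form as the main result, by multiple imputation from the other replies and the record data. State that it reduces bias but does not remove it.
- Optionally, best/worst-case bounds for the adverse-event proportion.

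If only one item is adopted, (a) is the cheapest and most useful, and it is itself descriptive.

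The cost is a few sentences, one table and one extra estimate, with no new data. The downside is a second, assumption-dependent figure beside the observed one, which will change little if response is high. The table can also miss weak dependence, so an unremarkable table should not be read as proof that replies are missing at random.

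### Do the 50/40/30 site quotas, pooled without weights or intervals, undermine the national description and the planning of the later trial?

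*Protocol*

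**What the plan says.** Under Data Processing and statistics the protocol calls the sample size one of convenience and ties each site's commitment to its annual number of elective caesareans: "Larger sites (>300 elective CS per year) commits to include 50 patients", medium sites (200 to 300 a year) 40, and "smaller sites (<200 elective CS per year) commits to include 30 patients". Number of participants asks for at least 400 patients from at least nine centres covering all five regions.

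The analysis is descriptive. "Continuous data will be summarized as median (interquartile range) or mean if the data is normally distributed"; categorical data are given as counts with percentages. One breakdown is named: "We plan to do a subgroup analysis on the groups where intrathecal morphine or TQL block has been administered". No weight, by-site estimate or confidence interval is mentioned.

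The Objective gives two uses for the results. "This study aims to map postoperative pain in Danish patients undergoing elective cesarean section", and "data from this observational study will also be used to inform a randomized controlled multicenter trial", the latter on the basis of response rates and of how often outcomes occur. The Outcomes section adds: "Outcomes have been selected to align with the outcomes in a subsequent randomized controlled multicenter trial".

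**The concern.** The quotas differ at most 1.67-fold (50/30), while the top band has no ceiling and the bottom band no floor. A patient at a small hospital can therefore be more likely to be sampled than one at a very large hospital. At assumed volumes of 100 and 600 a year the fractions are 30/100 = 30.0% and 50/600 = 8.3%, a ratio of 3.6. If pain or adverse events differ by hospital size, pooled unweighted figures lean towards the smaller sites.

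The protocol gives some reason to expect differences between hospitals. The Background says that the usual pain regimen matches most hospitals' protocols, which implies exceptions, and a subgroup analysis is planned for intrathecal morphine or TQL block.

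Two further points add to the impression. No interval shows how firm the planning values are. Read literally, the rule for continuous data gives either a median with IQR or a mean alone, so no standard deviation for the 24-hour pain score. The sample size of a trial with a continuous outcome scales with the square of the SD, so an SD wrong by 20% changes it by 36% (0.8² = 0.64) to 44% (1.2² = 1.44).

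At stake would be a national description that fits the quota mix better than the patients, and planning values that look firmer than they are.

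**Working it through.** **Inputs.** From the protocol: quotas 50/40/30, volume limits 200 and 300 a year, at least 400 patients, at least nine centres. Not in the protocol, hence assumed: site volumes (large 301, 500 or 600 a year; medium 250; small 150), the outcome gap between large and other sites (20 points), and the intraclass correlation (0.01 or 0.05). The quotas are treated as final counts, although the stated minimum of 400 and the wish for as large a study as possible suggest that they may be floors.

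**1. Can nine sites reach 400?** With L large and S small sites among nine, the quota total is 360 + 10 × (L − S). It runs from 270 to 450 and reaches 400 when L − S ≥ 4. That holds for 12 of the 55 possible mixes, none with more than two small sites. So 400 is attainable, and any nine-site mix that attains it through quotas alone contains few small sites.

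**2. Sampling fractions** (quota / annual volume).

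| Volume a year | Quota | Fraction |
|---|---|---|
| 150 | 30 | 20.0% |
| 199 | 30 | 15.1% |
| 250 | 40 | 16.0% |
| 300 | 40 | 13.3% |
| 301 | 50 | 16.6% |
| 600 | 50 | 8.3% |

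The bands follow volume roughly. Departures become large only at very small or very large hospitals.

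**3. Shift of the crude rate.** Shift = gap × (large sites' share of volume − large sites' share of sample). For five large, three medium and one small site the sample share is 250/400 = 0.625. The volume share is 1505/2405 = 0.626 at 301 a year, 2500/3400 = 0.735 at 500 and 3000/3900 = 0.769 at 600. A 20-point gap then gives:

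| Mix (large/medium/small) | 301 a year | 500 a year | 600 a year |
|---|---|---|---|
| 5/3/1 | 0.0 | 2.2 | 2.9 |
| 4/5/0 | −0.2 | 2.3 | 3.2 |
| 6/1/2 | 0.3 | 1.9 | 2.3 |

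A 10-point gap halves these figures. With nine large sites of equal volume, or with no relation between outcome and size, the shift is zero. For pain, a gap of one NRS point at the most unfavourable entry (4/5/0 at 600 a year: 2400/3650 − 200/400 = 0.158) moves the mean by about 0.16 points.

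**4. Precision.** For a rate near 50% and n = 400, the 95% half-width is 1.96 × √(0.25/400) = 4.9 points.

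- *Sites as strata* (inference to the participating hospitals): no design effect for clustering applies. The Kish weighting factor for the 5/3/1 mix is 1.003 at 301 a year and 1.09 at 600, so the weighted half-width is 4.9 to 5.1 points.
- *Sites as a sample of Danish hospitals*: the design effect is 1 + (Σm²/400 − 1) × ICC, with Σm² = 5 × 50² + 3 × 40² + 30² = 18,200. It is 1 + 44.5 × 0.01 = 1.445 or 1 + 44.5 × 0.05 = 3.225. The half-widths are 4.9 × √1.445 = 5.9 and 4.9 × √3.225 = 8.8 points (6.9 and 10.4 with t on 8 df, 2.306 in place of 1.96).

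This widening comes from clustering and would also arise with exactly proportional quotas.

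**5. By-site estimates.** 1.96 × √(0.25/m) gives 17.9, 15.5 and 13.9 points for m = 30, 40 and 50. Such tables can show spread between hospitals but cannot fix any one hospital's rate.

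**The case for a change.** The strongest case for the concern is that the protocol does more than stay silent: it writes out both the sampling scheme and the summaries, and it states a national aim and a planning aim. Quotas without a ceiling at the top or a floor at the bottom cannot track volume. A bias of 2 to 3 points is not harmless merely because it is smaller than the sampling error. Mean and SD, intervals with a stated basis for site, and a volume-weighted sensitivity estimate would take a few sentences.

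Part of this stands. The quotas are stepped, the named summaries are unweighted, and a reader should take them as describing the included patients. The rest does not amount to a fault:

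- A bias needs hospital volumes spread well beyond the band limits and also outcomes that vary with hospital size. The protocol gives no site volumes. Its hint that treatment differs between hospitals does not link this to size.
- The SD point carries little weight. The Objective bases the later trial on response rates and on how often outcomes occur, which counts and percentages supply. The investigators also hold the patient-level data in REDCap and can compute any SD they need.
- Volume weighting is a debatable choice here. Sites join voluntarily, so weights cannot speak for hospitals that stay out, and they leave selection by consent, language and smartphone untouched. A weight also needs each site's actual annual count, whereas the quota needs only its band.

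**Conclusion.** The concern does not hold. The protocol openly describes a convenience sample with volume-banded quotas and descriptive summaries. It claims neither proportional sampling nor volume-representative estimates, so no statement is wrong and no two passages conflict. Intervals, the treatment of site, by-site tables and the SD are commonly left to a statistical analysis plan, which is not among the documents at hand; their absence from the protocol is no defect.

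The conclusion does not rest on size alone, but the size agrees with it. Even a 20-point gap placed wholly between large and other sites shifts the crude rate by −0.2 to 3.2 points in the worked mixes, against a simple half-width of 4.9. These figures depend on assumed volumes of 150 to 600 a year and on quotas being final counts. The wider half-widths of 5.9 to 10.4 points depend on assumed ICCs and on treating the sites as a sample of Danish hospitals; they do not come from the quotas. What remains is a preference about reporting.

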Region Zealand (Region Sjælland): Roskilde

Region of Southern Denmark (Region Syd): Kolding, Odense

Central Denmark Region (Region Midt): Aarhus

North Denmark Region (Region Nord): Aalborg

The study is open for all Danish hospitals, where elective cesarean sections are performed. If any additional hospitals should wish to participate in the study within the specified time period, they will be included.

Data to be collected from the patient's medical record

Patient characteristics

- Pre-pregnancy BMI
- Parity
- Indication for cesarean section: Maternal request/Previous cesarean section as the only indication/Breech presentation/Maternal indication/Obstetric indication/Fetal indication/Other indication.
- Previous number of cesarean sections: 0, 1, 2, 3, or ≥ 4
- Previous abdominal surgeries: Yes/No. If yes: Laparoscopic or laparotomy
- Chronic pain patient (receiving regular opioid or other pain treatment besides NSAIDs and PCM) within 0-2 months prior to cesarean section: Yes/No
- Inflammatory bowel disease (Crohn's disease or ulcerative colitis): Yes/No
- Pregnancy-related illness? No/Gestational hypertensive disorder (Preeclampsia including HELLP, Gestational hypertension)/Gestational diabetes, Other.

Anesthesia information

- Spinal anesthesia: Bupivacaine, sufentanil, fentanyl, morphine. Mg and ml.
- Was the patient given an epidural-spinal? Yes/No
- Was general anesthesia administered as the initial preference for the patient? Yes/No
- Was the spinal anesthesia converted to epidural? Yes/No
- Was the spinal anesthesia converted to general anesthesia? Yes/No
- Was the spinal repeated following a failed spinal? Yes/No
- Was it necessary to supplement the spinal anesthesia with opioids, nitrous oxide, or similar due to breakthrough pain during the operation? Yes/No
- Did the patient have an epidural when going to the maternity ward after the recovery period? Yes/No. If yes: When was the epidural discontinued? Date and Time.

Operation information

- Operation time (minutes)
- Intraoperative bleeding. ml.
- Has the uterus been exteriorized during the operation? Yes/No/The information was not found in the medical record.
- Postoperative bleeding within the first 48 hours requiring blood transfusion. Yes/No
- Reoperation within the first 30 days: Yes/No. If yes: Abdominal bleeding/Vaginal bleeding/Suspected retained tissue or endometritis/Infection at the incision site/other reason

Pain management

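### The listed conversion items take no reason, so the insufficient-spinal composite cannot be derived cleanly from the listed data (minor)

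*Protocol*

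**What the plan says.** Protocol, Outcome measures, maternal secondary outcomes: the outcome is "Insufficient spinal anesthesia related adverse events during the caesarean section, as binary composite outcome", taken from the medical record. Its components are patients "in need of conversion to general anesthesia, intraoperative opioids, sevoflurane, or nitrous oxide for intraoperative pain", or with a "repeated neuraxial procedure (spinal or epidural placement following failed spinal".

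Protocol, Data to be collected from the patient's medical record, Anesthesia information: four items feed this composite.

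- General anesthesia, with no cause named: "Was the spinal anesthesia converted to general anesthesia? Yes/No"
- Epidural, with no cause named: "Was the spinal anesthesia converted to epidural? Yes/No"
- Intraoperative supplementation, with the cause named and also answered Yes/No: "Was it necessary to supplement the spinal anesthesia with opioids, nitrous oxide, or similar due to breakthrough pain during the operation"
- Second spinal, with the cause named: "Was the spinal repeated following a failed spinal? Yes/No"

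The same list has separate items for a planned epidural-spinal and for general anesthesia as the initial choice. Under Pain management, a reason is listed for nerve blocks and for epidurals placed within the first 24 hours after the section. The extraction sheet itself is named as Appendix 3, and its content is not shown.

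**The concern.** The outcome is meant to describe how often the spinal block was insufficient, so each component needs to be tied to that cause, either in the definition or in the data item. Two of the four items are tied to it and two are not. A woman whose spinal works but who is converted to general anesthesia because of bleeding receives the same Yes as a woman whose block failed.

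Two things are at stake. First, the composite may mix surgical events with block quality, and by this route the reported rate can only move upwards. Second, each hospital has its own data manager. With no reason field, one may answer the item literally while another applies the outcome definition, so sites may differ for reasons unrelated to the block. A later analysis plan can define a derivation, but it cannot use a reason that was never collected.

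**Working it through.** The plan states no rate, power or precision for this outcome, so there is no figure to reproduce. The check sets each component against its data item and then bounds the size under stated assumptions.

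**Definition against data item**

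| Component | Cause in the outcome definition | Cause in the listed item |
|---|---|---|
| Conversion to general anesthesia | Only through the outcome's name; the pain qualifier closes the list, and it is unclear whether it reaches back to this component | None |
| Intraoperative opioid, sevoflurane or nitrous oxide | Intraoperative pain | Breakthrough pain |
| Repeat spinal | Failed spinal | Failed spinal |
| Epidural | Failed spinal | None |

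The gap is clearest for general anesthesia, where neither the component wording nor the item fixes the cause. For the epidural the definition is clear, and only the item drops the condition.

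**Can other listed fields supply the reason?** Operation time and intraoperative bleeding are listed, but they are only proxies. A high blood loss does not show that the conversion was made because of it. The reason listed under Pain management belongs to epidurals placed after the section. Nothing equivalent is listed for general anesthesia.

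**Size, on assumed inputs**

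Inputs:

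- N = 400, the planned minimum (Protocol, Number of participants).
- c, the share of women converted to general anesthesia: assumed 0.5% to 3%.
- s, the share of those conversions made for a cause other than insufficient spinal, in women with no other qualifying event: assumed 10% to 50%.
- p, the true composite rate: assumed 5%, 10% or 20%.

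Only N comes from the documents.

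Excess rate = c × s.

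- Low end: 0.005 × 0.10 = 0.0005, or 0.05 points; 400 × 0.0005 = 0.2 women.
- High end: 0.03 × 0.50 = 0.015, or 1.5 points; 400 × 0.015 = 6 women.

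95% half-width = 1.96 × √(p(1 − p)/400). Relative excess = c × s / p.

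| p | Half-width | Relative excess |
|---|---|---|
| 5% | 1.96 × √(0.0475/400) = 2.1 points | 0.05/5 = 1% to 1.5/5 = 30% |
| 10% | 1.96 × √(0.09/400) = 2.9 points | 0.05/10 = 0.5% to 1.5/10 = 15% |
| 20% | 1.96 × √(0.16/400) = 3.9 points | 0.05/20 = 0.25% to 1.5/20 = 7.5% |

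The largest excess, 1.5 points, stays below the smallest half-width, 2.1 points. The 30% combines the highest c, the highest s and the lowest p, and should not be relied on.

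**The case against.** The strongest reply is that the definition already restricts the outcome by name, so an extractor or analyst who follows it would not count a conversion for bleeding. This stands in part. A reader might infer that any switch away from the spinal counts, but that is not the stated rule. The mismatch lies between the definition and the listed items. It does not remove the point, because with only a bare Yes the restriction cannot be applied or checked afterwards.

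The epidural half is weaker, since the definition requires placement after a failed spinal. A reader might also worry that later use of a catheter from a planned epidural-spinal would be scored as a failure. Those women have their own item and can be identified, and use of an existing catheter does not meet the definition. That such cases would be entered as conversions is speculation.

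Reoperation might seem another source of error. The outcome is confined to events during the caesarean itself, and reoperation has its own item with reasons, so it does not belong here. Conversion after prolonged surgery is not a clear misclassification either: if the block wore off, that is arguably an insufficient spinal.

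Appendix 3 is not shown, so it cannot be claimed that the form itself omits a reason, only that the protocol's list does.

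Finally, this is one secondary outcome in a descriptive convenience cohort, with no test or power attached, and the assumed excess lies within sampling error. That limits the severity. It does not cancel the bias, because a confidence interval does not reflect misclassification and more patients would not shrink it.

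**Conclusion.** The point holds in a narrow form. As listed, the item for conversion to general anesthesia, and to a lesser degree the item for conversion to epidural, does not record whether the switch was made for insufficient spinal anesthesia. The composite as named therefore cannot be derived cleanly. If the items are used as written, the error runs upwards only.

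Its size cannot be established from the documents. The range of 0.05 to 1.5 points rests wholly on assumed conversion shares, assumed causes and the absence of another qualifying event in the women concerned. It is probably small.

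A reader might infer that this outcome will supply the event rate for the later randomised trial. The protocol goes less far: outcome frequencies are to inform that trial, and outcomes were chosen to align with it. It does not say that this outcome will size it, and the trial's stated question is postoperative pain control with intrathecal morphine, whereas this outcome is intraoperative. Severity is minor.

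**What to change.** Add one reason field (inadequate block or pain / other / not found) to the general anesthesia and epidural conversion items, completed only when the answer is Yes. If Appendix 3 already takes a reason, align the protocol's list with it instead. Add a sentence to the outcome definition that a conversion enters the composite only when the reason is inadequate block or pain. Report conversions for other reasons, and those with no reason found, separately.

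The cost is two drop-down items in REDCap, one sentence of text, slightly more chart reading for a few women, and some entries with no reason found. Because the source is the medical record, the reason could also be looked up for women already included. Clinical care is unaffected.
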